14.3.1.2.5 Unsolicited Adverse Events Within 28 Days After any Dose, Safety Analysis Set

System organ class	CV7202	CV7202	CV7202	Rabipur	Total
Preferred term [n (%) m]	1 µg (N = xx)	2 µg (N = xx)	5 µg (N = xx)	(N = xx)	(N = xx)
Any adverse events	xx (xx.x%) xxx	xx (xx.x%) xxx	xx (xx.x%) xxx	xx (xx.x%) xxx	xx (xx.x%) xxx
System organ class 1	xx (xx.x%) xxx	xx (xx.x%) xxx	xx (xx.x%) xxx	xx (xx.x%) xxx	xx (xx.x%) xxx
Preferred term 1	xx (xx.x%) xxx	xx (xx.x%) xxx	xx (xx.x%) xxx	xx (xx.x%) xxx	xx (xx.x%) xxx
Preferred term 2	xx (xx.x%) xxx	xx (xx.x%) xxx	xx (xx.x%) xxx	xx (xx.x%) xxx	xx (xx.x%) xxx
Preferred term 3	xx (xx.x%) xxx	xx (xx.x%) xxx	xx (xx.x%) xxx	xx (xx.x%) xxx	xx (xx.x%) xxx
Preferred term 4	xx (xx.x%) xxx	xx (xx.x%) xxx	xx (xx.x%) xxx	xx (xx.x%) xxx	xx (xx.x%) xxx
...	xx (xx.x%) xxx	xx (xx.x%) xxx	xx (xx.x%) xxx	xx (xx.x%) xxx	xx (xx.x%) xxx
System organ class 2	xx (xx.x%) xxx	xx (xx.x%) xxx	xx (xx.x%) xxx	xx (xx.x%) xxx	xx (xx.x%) xxx
Preferred term 1	xx (xx.x%) xxx	xx (xx.x%) xxx	xx (xx.x%) xxx	xx (xx.x%) xxx	xx (xx.x%) xxx
Preferred term 2	xx (xx.x%) xxx	xx (xx.x%) xxx	xx (xx.x%) xxx	xx (xx.x%) xxx	xx (xx.x%) xxx
Preferred term 3	xx (xx.x%) xxx	xx (xx.x%) xxx	xx (xx.x%) xxx	xx (xx.x%) xxx	xx (xx.x%) xxx
...	xx (xx.x%) xxx	xx (xx.x%) xxx	xx (xx.x%) xxx	xx (xx.x%) xxx	xx (xx.x%) xxx

n = Number of subjects; m = Number of events; AEs on the day of vaccination and 28 subsequent days
 Adverse events were coded using MedDRA version 24.1. At each level of summation (system organs class, preferred term) subjects reporting more than 1 event are included only once.

Table is sorted by descending subject count in the total column by system organ class and preferred term.
 Percentages are based on total number of subjects in each vaccination group

PROGRAM SOURCE: tlf-###, DATA CUT OFF DATE: DDMMYYYY

RUN DATE: DDMMYYYY hh:mm

Programming note:

*Sort by decreasing frequency of the total column by SOC and preferred term.
 According to the SAP all unsolicited AE tables will be restricted to adverse events that occurred AFTER the first administration of the trial vaccine (post vaccination). If adverse events BEFORE are documented, they will be flagged and listed only.*

Sponsor
Protocol number

Clinical Study Report
Page x of y

14.3.1.2.6 Unsolicited Adverse Events Within 28 Days Post Dose 1, Safety Analysis Set

System organ class Preferred term [n (%) m]	CV7202 (N = xx)	CV7202 (N = xx)	CV7202 (N = xx)	Rabipur (N = xx)	Total (N = xx)
Any adverse events	xx (xx.x%) xxx	xx (xx.x%) xxx			
System organ class 1	xx (xx.x%) xxx	xx (xx.x%) xxx			
Preferred term 1	xx (xx.x%) xxx	xx (xx.x%) xxx			
Preferred term 2	xx (xx.x%) xxx	xx (xx.x%) xxx			
Preferred term 3	xx (xx.x%) xxx	xx (xx.x%) xxx			
Preferred term 4	xx (xx.x%) xxx	xx (xx.x%) xxx			
...	xx (xx.x%) xxx	xx (xx.x%) xxx			
System organ class 2	xx (xx.x%) xxx	xx (xx.x%) xxx			
Preferred term 1	xx (xx.x%) xxx	xx (xx.x%) xxx			
Preferred term 2	xx (xx.x%) xxx	xx (xx.x%) xxx			
Preferred term 3	xx (xx.x%) xxx	xx (xx.x%) xxx			
...	xx (xx.x%) xxx	xx (xx.x%) xxx			

n = Number of subjects; m = Number of events;

AEs on the day of vaccination and 28 subsequent days, but before 2nd CV7202 or 3rd Rabipur vaccination.

Adverse events were coded using MedDRA version 24.1. At each level of summation (system organs class, preferred term) subjects reporting more than 1 event are included only once.

Table is sorted by descending subject count in the total column by system organ class and preferred term.

Percentages are based on total number of subjects in each vaccination group

PROGRAM SOURCE: tlif-###, DATA CUT OFF DATE: DDMMYYYY

RUN DATE: DDMMYYYY hh:mm

Programming note:

Sort by decreasing frequency of the total column by SOC and preferred term.

According to the SAP all unsolicited AE tables will be restricted to adverse events that occurred AFTER the first administration of the trial vaccine (post vaccination). If adverse events BEFORE are documented, they will be flagged and listed only.

Sponsor

Clinical Study Report

Protocol number

Page x of y

14.3.1.2.7 Unsolicited Adverse Events Within 28 Days Post Dose 2 CV7202 or Dose 3 Rabipur, Safety Analysis Set

System organ class Preferred term [n (%) m]	CV7202 2x1 µg (N = xx)	CV7202 2x2 µg (N = xx)	Rabipur (N = xx)	Total (N = xx)
Any adverse events	xx (xx.x%) xxx	xx (xx.x%) xxx	xx (xx.x%) xxx	xx (xx.x%) xxx
System organ class 1	xx (xx.x%) xxx	xx (xx.x%) xxx	xx (xx.x%) xxx	xx (xx.x%) xxx
Preferred term 1	xx (xx.x%) xxx	xx (xx.x%) xxx	xx (xx.x%) xxx	xx (xx.x%) xxx
Preferred term 2	xx (xx.x%) xxx	xx (xx.x%) xxx	xx (xx.x%) xxx	xx (xx.x%) xxx
Preferred term 3	xx (xx.x%) xxx	xx (xx.x%) xxx	xx (xx.x%) xxx	xx (xx.x%) xxx
Preferred term 4	xx (xx.x%) xxx	xx (xx.x%) xxx	xx (xx.x%) xxx	xx (xx.x%) xxx
...	xx (xx.x%) xxx	xx (xx.x%) xxx	xx (xx.x%) xxx	xx (xx.x%) xxx
System organ class 2	xx (xx.x%) xxx	xx (xx.x%) xxx	xx (xx.x%) xxx	xx (xx.x%) xxx
Preferred term 1	xx (xx.x%) xxx	xx (xx.x%) xxx	xx (xx.x%) xxx	xx (xx.x%) xxx
Preferred term 2	xx (xx.x%) xxx	xx (xx.x%) xxx	xx (xx.x%) xxx	xx (xx.x%) xxx
Preferred term 3	xx (xx.x%) xxx	xx (xx.x%) xxx	xx (xx.x%) xxx	xx (xx.x%) xxx
...	xx (xx.x%) xxx	xx (xx.x%) xxx	xx (xx.x%) xxx	xx (xx.x%) xxx

n = Number of subjects; m = Number of events;

AEs on the day of vaccination and 28 subsequent days.

Adverse events were coded using MedDRA version 24.1. At each level of summation (system organs class, preferred term) subjects reporting more than 1 event are included only once.

Table is sorted by descending subject count in the total column by system organ class and preferred term.

Percentages are based on total number of subjects in each vaccination group

PROGRAM SOURCE: tlif-###, DATA CUT OFF DATE: DDMMYYYY

RUN DATE: DDMMYYYY hh:mm

Programming note:

Sort by decreasing frequency of the total column by SOC and preferred term.

According to the SAP all unsolicited AE tables will be restricted to adverse events that occurred AFTER the first administration of the trial vaccine (post vaccination). If adverse events BEFORE are documented, they will be flagged and listed only.

Sponsor

Clinical Study Report

Page x of y

Protocol number

14.3.1.3.1 Overall Summary of Unsolicited Adverse Events for the Duration of the Trial After any Dose, Safety Analysis Set

Adverse Event Category [n (%) m]	CV7202 1 µg (N = xx)	CV7202 2 µg (N = xx)	CV7202 5 µg (N = xx)	Rabipur (N = xx)
All unsolicited adverse events	xx (xx.x%) xxx	xx (xx.x%) xxx	xx (xx.x%) xxx	xx (xx.x%) xxx
Related unsolicited adverse events	xx (xx.x%) xxx	xx (xx.x%) xxx	xx (xx.x%) xxx	xx (xx.x%) xxx
Serious adverse events	xx (xx.x%) xxx	xx (xx.x%) xxx	xx (xx.x%) xxx	xx (xx.x%) xxx
Related serious adverse events	xx (xx.x%) xxx	xx (xx.x%) xxx	xx (xx.x%) xxx	xx (xx.x%) xxx
Medically attended adverse events	xx (xx.x%) xxx	xx (xx.x%) xxx	xx (xx.x%) xxx	xx (xx.x%) xxx
Adverse events leading to withdrawal from study	xx (xx.x%) xxx	xx (xx.x%) xxx	xx (xx.x%) xxx	xx (xx.x%) xxx
Adverse events leading to discontinued vaccination	xx (xx.x%) xxx	xx (xx.x%) xxx	xx (xx.x%) xxx	xx (xx.x%) xxx
Adverse events of special interest	xx (xx.x%) xxx	xx (xx.x%) xxx	xx (xx.x%) xxx	xx (xx.x%) xxx

n = Number of subjects; m = Number of events; AEs on the day of vaccination and all subsequent days

Subjects reporting more than 1 event are counted only once for the subject count.

Percentages are based on total no. of subjects in each vaccination group.

Related: Adverse events which were assessed by the investigator as related to trial vaccine or study procedure.

PROGRAM SOURCE: tlf-###, DATA CUT OFF DATE: DDMMYYYY

RUN DATE: DDMMYYYY hh:mm

Programming note:

According to the SAP all unsolicited AE tables will be restricted to adverse events that occurred AFTER the first administration of the trial vaccine. If adverse events BEFORE are documented, these will be flagged and listed only.

Sponsor

Clinical Study Report

Page x of y

Protocol number

14.3.1.3.2 Summary of Unsolicited Adverse Events for the Duration of the Trial by Maximum Intensity (Grade) After any Dose, Safety Analysis Set

Adverse Event Category [n (%)]		CV7202 1x1 µg (N = xx)	CV7202 2x1 µg (N = xx)	CV7202 1x2 µg (N = xx)	CV7202 2x2 µg (N = xx)
All unsolicited adverse events	Mild (grade 1)	xx (xx.x%)	xx (xx.x%)	xx (xx.x%)	xx (xx.x%)
	Moderate (grade 2)	xx (xx.x%)	xx (xx.x%)	xx (xx.x%)	xx (xx.x%)
	Severe (grade 3)	xx (xx.x%)	xx (xx.x%)	xx (xx.x%)	xx (xx.x%)
Related unsolicited adverse events	Mild (grade 1)	xx (xx.x%)	xx (xx.x%)	xx (xx.x%)	xx (xx.x%)
	Moderate (grade 2)	xx (xx.x%)	xx (xx.x%)	xx (xx.x%)	xx (xx.x%)
	Severe (grade 3)	xx (xx.x%)	xx (xx.x%)	xx (xx.x%)	xx (xx.x%)

n = Number of subjects; AEs on the day of vaccination and all subsequent days

Subjects reporting more than 1 event are counted only once for the subject count with highest intensity (grade).

Percentages are based on total no. of subjects in each vaccination group.

Related: Adverse events which were assessed by the investigator as related to trial vaccine or study procedure.

PROGRAM SOURCE: tlf-###, DATA CUT OFF DATE: DDMMYYYY

RUN DATE: DDMMYYYY hh:mm

Programming note:

According to the SAP all unsolicited AE tables will be restricted to adverse events that occurred AFTER the first administration of the trial vaccine. If adverse events BEFORE are documented, these will be flagged and listed only.

Sponsor

Clinical Study Report

Protocol number

Page x of y

14.3.1.3.3 Unsolicited Adverse Events for the Duration of the Trial After any Dose, Safety Analysis Set

System organ class Preferred term [n (%) m]	CV7202 1 µg (N = xx)	CV7202 2 µg (N = xx)	CV7202 5 µg (N = xx)	Rabipur (N = xx)	Total (N = xx)
Any adverse events	xx (xx.x%) xxx	xx (xx.x%) xxx	xx (xx.x%) xxx	xx (xx.x%) xxx	xx (xx.x%) xxx
System organ class 1	xx (xx.x%) xxx	xx (xx.x%) xxx	xx (xx.x%) xxx	xx (xx.x%) xxx	xx (xx.x%) xxx
Preferred term 1	xx (xx.x%) xxx	xx (xx.x%) xxx	xx (xx.x%) xxx	xx (xx.x%) xxx	xx (xx.x%) xxx
Preferred term 2	xx (xx.x%) xxx	xx (xx.x%) xxx	xx (xx.x%) xxx	xx (xx.x%) xxx	xx (xx.x%) xxx
Preferred term 3	xx (xx.x%) xxx	xx (xx.x%) xxx	xx (xx.x%) xxx	xx (xx.x%) xxx	xx (xx.x%) xxx
Preferred term 4	xx (xx.x%) xxx	xx (xx.x%) xxx	xx (xx.x%) xxx	xx (xx.x%) xxx	xx (xx.x%) xxx
...	xx (xx.x%) xxx	xx (xx.x%) xxx	xx (xx.x%) xxx	xx (xx.x%) xxx	xx (xx.x%) xxx
System organ class 2	xx (xx.x%) xxx	xx (xx.x%) xxx	xx (xx.x%) xxx	xx (xx.x%) xxx	xx (xx.x%) xxx
Preferred term 1	xx (xx.x%) xxx	xx (xx.x%) xxx	xx (xx.x%) xxx	xx (xx.x%) xxx	xx (xx.x%) xxx
Preferred term 2	xx (xx.x%) xxx	xx (xx.x%) xxx	xx (xx.x%) xxx	xx (xx.x%) xxx	xx (xx.x%) xxx
Preferred term 3	xx (xx.x%) xxx	xx (xx.x%) xxx	xx (xx.x%) xxx	xx (xx.x%) xxx	xx (xx.x%) xxx
...	xx (xx.x%) xxx	xx (xx.x%) xxx	xx (xx.x%) xxx	xx (xx.x%) xxx	xx (xx.x%) xxx

n = Number of subjects; m = Number of events; AEs on the day of vaccination and all subsequent days

Adverse events were coded using MedDRA version 24.1. At each level of summation (system organs class, preferred term) subjects reporting more than 1 event are included only once.

Table is sorted by descending subject count in the total column by system organ class and preferred term.

Percentages are based on total number of subjects in each vaccination group

PROGRAM SOURCE: tlf-###, DATA CUT OFF DATE: DDMMYYYY

RUN DATE: DDMMYYYY hh:mm

Programming note:

Sort by decreasing frequency of the total column by SOC and preferred term.

According to the SAP all unsolicited AE tables will be restricted to adverse events that occurred AFTER the first administration of the trial vaccine (post vaccination). If adverse events BEFORE are documented, they will be flagged and listed only.

Sponsor

Clinical Study Report

Protocol number

Page x of y

14.3.1.3.4 Unsolicited Adverse Events for the Duration of the Trial Post Dose 1, Safety Analysis Set

System organ class Preferred term [n (%) m]	CV7202 1x1 µg (N = xx)	CV7202 1x2 µg (N = xx)	CV7202 5 µg (N = xx)	Total (N = xx)
Any adverse events	xx (xx.x%) xxx	xx (xx.x%) xxx	xx (xx.x%) xxx	xx (xx.x%) xxx
System organ class 1	xx (xx.x%) xxx	xx (xx.x%) xxx	xx (xx.x%) xxx	xx (xx.x%) xxx
Preferred term 1	xx (xx.x%) xxx	xx (xx.x%) xxx	xx (xx.x%) xxx	xx (xx.x%) xxx
Preferred term 2	xx (xx.x%) xxx	xx (xx.x%) xxx	xx (xx.x%) xxx	xx (xx.x%) xxx
Preferred term 3	xx (xx.x%) xxx	xx (xx.x%) xxx	xx (xx.x%) xxx	xx (xx.x%) xxx
Preferred term 4	xx (xx.x%) xxx	xx (xx.x%) xxx	xx (xx.x%) xxx	xx (xx.x%) xxx
...	xx (xx.x%) xxx	xx (xx.x%) xxx	xx (xx.x%) xxx	xx (xx.x%) xxx
System organ class 2	xx (xx.x%) xxx	xx (xx.x%) xxx	xx (xx.x%) xxx	xx (xx.x%) xxx
Preferred term 1	xx (xx.x%) xxx	xx (xx.x%) xxx	xx (xx.x%) xxx	xx (xx.x%) xxx
Preferred term 2	xx (xx.x%) xxx	xx (xx.x%) xxx	xx (xx.x%) xxx	xx (xx.x%) xxx
Preferred term 3	xx (xx.x%) xxx	xx (xx.x%) xxx	xx (xx.x%) xxx	xx (xx.x%) xxx
...	xx (xx.x%) xxx	xx (xx.x%) xxx	xx (xx.x%) xxx	xx (xx.x%) xxx

n = Number of subjects; m = Number of events;

AEs on the day of vaccination and all subsequent days.

Adverse events were coded using MedDRA version 24.1. At each level of summation (system organs class, preferred term) subjects reporting more than 1 event are included only once.

Table is sorted by descending subject count in the total column by system organ class and preferred term.

Percentages are based on total number of subjects in each vaccination group

PROGRAM SOURCE: tlif-###, DATA CUT OFF DATE: DDMMYYYY

RUN DATE: DDMMYYYY hh:mm

Programming note:

Sort by decreasing frequency of the total column by SOC and preferred term.

According to the SAP all unsolicited AE tables will be restricted to adverse events that occurred AFTER the first administration of the trial vaccine (post vaccination). If adverse events BEFORE are documented, they will be flagged and listed only.

Sponsor

Clinical Study Report

Page x of y

Protocol number

14.3.1.3.5 Unsolicited Adverse Events for the Duration of the Trial Post Dose 2 CV7202 or Dose 3 Rabipur, Safety Analysis Set

System organ class Preferred term [n (%) m]	CV7202 2x1 µg (N = xx)	CV7202 2x2 µg (N = xx)	Rabipur (N = xx)	Total (N = xx)
Any adverse events	xx (xx.x%) xxx	xx (xx.x%) xxxx	xx (xx.x%) xxxx	xx (xx.x%) xxxx
System organ class 1	xx (xx.x%) xxx	xx (xx.x%) xxxx	xx (xx.x%) xxxx	xx (xx.x%) xxxx
Preferred term 1	xx (xx.x%) xxx	xx (xx.x%) xxxx	xx (xx.x%) xxxx	xx (xx.x%) xxxx
Preferred term 2	xx (xx.x%) xxx	xx (xx.x%) xxxx	xx (xx.x%) xxxx	xx (xx.x%) xxxx
Preferred term 3	xx (xx.x%) xxx	xx (xx.x%) xxxx	xx (xx.x%) xxxx	xx (xx.x%) xxxx
Preferred term 4	xx (xx.x%) xxx	xx (xx.x%) xxxx	xx (xx.x%) xxxx	xx (xx.x%) xxxx
...	xx (xx.x%) xxx	xx (xx.x%) xxxx	xx (xx.x%) xxxx	xx (xx.x%) xxxx
System organ class 2	xx (xx.x%) xxx	xx (xx.x%) xxxx	xx (xx.x%) xxxx	xx (xx.x%) xxxx
Preferred term 1	xx (xx.x%) xxx	xx (xx.x%) xxxx	xx (xx.x%) xxxx	xx (xx.x%) xxxx
Preferred term 2	xx (xx.x%) xxx	xx (xx.x%) xxxx	xx (xx.x%) xxxx	xx (xx.x%) xxxx
Preferred term 3	xx (xx.x%) xxx	xx (xx.x%) xxxx	xx (xx.x%) xxxx	xx (xx.x%) xxxx
...	xx (xx.x%) xxx	xx (xx.x%) xxxx	xx (xx.x%) xxxx	xx (xx.x%) xxxx

n = Number of subjects; m = Number of events; AEs on the day of vaccination and all subsequent days
Adverse events were coded using MedDRA version 24.1. At each level of summation (system organs class, preferred term) subjects reporting more than 1 event are included only once.
Table is sorted by descending subject count in the total column by system organ class and preferred term.
Percentages are based on total number of subjects in each vaccination group

PROGRAM SOURCE: tlif-###, DATA CUT OFF DATE: DDMMYYYY

RUN DATE: DDMMYYYY hh:mm

Programming note:

Sort by decreasing frequency of the total column by SOC and preferred term.

According to the SAP all unsolicited AE tables will be restricted to adverse events that occurred AFTER the first administration of the trial vaccine (post vaccination). If adverse events BEFORE are documented, they will be flagged and listed only.

Sponsor

Clinical Study Report

Protocol number

Page x of y

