6. GENERAL ANALYSIS CONSIDERATIONS

The statistical analyses will be reported using summary tables, listings, and figures (TLFs). The International Council for Harmonisation (ICH) numbering convention will be used for all TLFs. Due to the exploratory nature of this trial, only descriptive statistics will be used; therefore, no confirmatory statistical inference will be performed.

Continuous variables will be summarized with means, standard deviations, medians, minimums, maximums, and valid cases. Other summaries may be used as appropriate.

Categorical variables will be summarized by counts and by percentage of subjects in corresponding categories. Percentages for missing values are omitted and do not account for the percent calculation of other categories. Percentages are routinely based on the total category count excluding the missing category if not otherwise mentioned. Percentages showing a rate relative to the total number of subjects in this group are given in special tables (eg, adverse event [AE] tables). Footnotes will specify the percent basis in those cases.

All summary tables will be presented by vaccination group (in the tables denoted as 'dosage/vaccine'). Baseline summaries will also include a total summary column. The CV7202 dose groups will be reported from the lowest to the highest dose. Selected tables will also display by dose regimen (in the tables denoted as 'treatment group').

Individual subject data obtained from the eCRFs or data from external sources like immunogenicity laboratory data and any derived data will be presented by subject in data listings. All post-baseline unscheduled assessments will be listed only. Only scheduled post-baseline safety measurements will be summarized, if appropriate. Should a repeat occur at a scheduled visit then only the last result per visit will be considered for the summary tables.

The analyses described in this plan are considered a priori, in that they have been defined prior to database lock. Any analyses performed subsequent to finalization of this statistical analysis plan will be considered post hoc and exploratory. Post hoc analyses will be labeled as such on the output and identified in the clinical trial report.

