11.2.2 Unsolicited Adverse Events

Serious AEs, intercurrent medical conditions, AEs leading to trial or vaccine withdrawal, AEs of special interest (AESIs) and MAAEs will be collected by the investigator in the eCRF throughout the trial.

AEs with a suspected potential immune-mediated disease etiology will be considered AESIs. The investigator will assess if an AE is an AESI. A list of AESIs is provided in Appendix 10 of the protocol.

AEs that are reported as related to the test vaccine will be considered trial vaccine-related; missing classifications concerning trial vaccine relationship will also be considered trial vaccine-related.

Every unsolicited AE will be assigned to a vaccination dose (number) by consideration of the period of 28 days after vaccination administration. Unsolicited AEs can be assigned to either day 1 to 28 (dose 1 for any vaccination group), or day 29 to 57 (dose 2 for 2-dose regimens or dose 3 for the Rabipur group). For the Rabipur group, vaccination dose 2 is administered 8 days after vaccination dose 1, therefore no assignment of unsolicited AEs to vaccination dose 2 is done for the Rabipur group.

All AE summaries will be restricted to those AEs that occurred after the first administration of the trial product. Any other AE (ie, AE starting after trial entry and before the first vaccination) will be reflected only in the data listings. If it cannot be determined whether the AE occurred after the first administration of the trial product due to a partial onset date, then it will be counted as such. Verbatim terms in the eCRFs will be mapped to preferred terms (PTs) and system organ classes (SOCs) using the Medical Dictionary for Regulatory Activities (version 21.0 or higher).

The occurrence of unsolicited AEs reported on the day of vaccination and the 28 subsequent days will be presented. In addition selected AE summary tables will be repeated for unsolicited AEs occurring at any time after the first administration of the trial product.

Each AE summary will be displayed by vaccination group and dose regimen. Summaries by vaccination dose (number) will also be provided for all AEs. Summaries that are displayed by SOC and PT will be ordered by descending order of incidence of SOC and PT within each system organ class. Summaries will display number and percentage of subjects with at least 1 event and the number of events by vaccination group.

Summaries of the following types will be presented:

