14.3.1.1.4.1	Day of First Onset of Solicited Adverse Events Post Dose 1	Safety Analysis Set	
14.3.1.1.4.2	Day of First Onset of Solicited Adverse Events Post Dose 2	Safety Analysis Set	
14.3.1.1.4.3	Day of First Onset of Solicited Adverse Events Post Dose 3	Safety Analysis Set	
14.3.1.1.4.4	Day of First Onset of Local Solicited Adverse Events Post Dose 1	Safety Analysis Set	
14.3.1.1.4.5	Day of First Onset of Local Solicited Adverse Events Post Dose 2	Safety Analysis Set	
14.3.1.1.4.6	Day of First Onset of Local Solicited Adverse Events Post Dose 3	Safety Analysis Set	
14.3.1.1.4.7	Day of First Onset of Systemic Solicited Adverse Events Post Dose 1	Safety Analysis Set	
14.3.1.1.4.8	Day of First Onset of Systemic Solicited Adverse Events Post Dose 2	Safety Analysis Set	
14.3.1.1.4.9	Day of First Onset of Systemic Solicited Adverse Events Post Dose 3	Safety Analysis Set	
14.3.1.1.4.10	Day of First Onset of Related Systemic Solicited Adverse Events Post Dose 1	Safety Analysis Set	
14.3.1.1.4.11	Day of First Onset of Related Systemic Solicited Adverse Events Post Dose 2	Safety Analysis Set	
14.3.1.1.4.12	Day of First Onset of Related Systemic Solicited Adverse Events Post Dose 3	Safety Analysis Set	
14.3.1.2	Unsolicited Adverse Events Within 28 Days		
14.3.1.2.1	Overall Summary of Unsolicited Adverse Events Within 28 Days After any Dose	Safety Analysis Set	
14.3.1.2.2	Overall Summary of Unsolicited Adverse Events Within 28 Days Post Dose 1	Safety Analysis Set	
14.3.1.2.3	Overall Summary of Unsolicited Adverse Events Within 28 Days Post Dose 2 CV7202 or Dose 3 Rabipur	Safety Analysis Set	
14.3.1.2.4	Summary of Unsolicited Adverse Events Within 28 Days by Maximum Intensity (Grade) After any Dose	Safety Analysis Set	
14.3.1.2.5	Unsolicited Adverse Events Within 28 Days After any Dose	Safety Analysis Set	
14.3.1.2.6	Unsolicited Adverse Events Within 28 Days Post Dose 1	Safety Analysis Set	

Table Number	Table Title	Analysis Set	Comment
14.3.1.2.7	Unsolicited Adverse Events Within 28 Days Post Dose 2 CV7202 or Dose 3 Rabipur	Safety Analysis Set	
14.3.1.3	Unsolicited Adverse Events for the Duration of the Trial	Safety Analysis Set	
14.3.1.3.1	Overall Summary of Unsolicited Adverse Events for the Duration of the Trial after Any Dose	Safety Analysis Set	
14.3.1.3.2	Summary of Unsolicited Adverse Events for the Duration of the Trial by Maximum Intensity (Grade) after Any Dose	Safety Analysis Set	

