Percentages are based on total no. of subjects in each vaccination group.

Related: Adverse events which were assessed by the investigator as related to trial vaccine or study procedure.

PROGRAM SOURCE: tlf-###, DATA CUT OFF DATE: DDMMYYYY

RUN DATE: DDMMYYYY hh:mm

Programming note:

According to the SAP all unsolicited AE tables will be restricted to adverse events that occurred AFTER the first administration of the trial vaccine. If adverse events BEFORE are documented, these will be flagged and listed only.

Sponsor

Clinical Study Report

Page x of y

Protocol number

14.3.1.2.4 Summary of Unsolicited Adverse Events Within 28 Days by Maximum Intensity (Grade) After any Dose, Safety Analysis Set

Adverse Event Category [n (%)]	CV7202 1 µg (N = xx)	CV7202 2 µg (N = xx)	CV7202 5 µg (N = xx)	Rabipur (N = xx)
All unsolicited adverse events	Mild (grade 1) xx (xx.x%) Moderate (grade 2) xx (xx.x%) Severe (grade 3) xx (xx.x%)	xx (xx.x%) xx (xx.x%) xx (xx.x%)	xx (xx.x%) xx (xx.x%) xx (xx.x%)	xx (xx.x%) xx (xx.x%) xx (xx.x%)
Related unsolicited adverse events	Mild (grade 1) xx (xx.x%) Moderate (grade 2) xx (xx.x%) Severe (grade 3) xx (xx.x%)	xx (xx.x%) xx (xx.x%) xx (xx.x%)	xx (xx.x%) xx (xx.x%) xx (xx.x%)	xx (xx.x%) xx (xx.x%) xx (xx.x%)

n = Number of subjects; AEs on the day of vaccination and 28 subsequent days

Subjects reporting more than 1 event are counted only once for the subject count with highest intensity (grade).

Percentages are based on total no. of subjects in each vaccination group.

Related: Adverse events which were assessed by the investigator as related to trial vaccine or study procedure.

PROGRAM SOURCE: tlf-###, DATA CUT OFF DATE: DDMMYYYY

RUN DATE: DDMMYYYY hh:mm

Programming note:

According to the SAP all unsolicited AE tables will be restricted to adverse events that occurred AFTER the first administration of the trial vaccine. If adverse events BEFORE are documented, these will be flagged and listed only.

Sponsor
 Protocol number

 Clinical Study Report
 Page x of y

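### SAP shell 14.3.1.3.2, the only trial-long table of unsolicited AEs by maximum grade, has no 5 µg or Rabipur column, contrary to the SAP's own display rules

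*SAP*

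**What the plan says.** SAP section 6 sets the general rule: "All summary tables will be presented by vaccination group". It treats display by dose regimen as an addition for selected tables. Under SAP section 7 the vaccination groups are CV7202 1 µg, 2 µg, 5 µg and Rabipur, and the regimens subdivide the 1 µg and 2 µg groups only.

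Section 11.2.2 adds, for unsolicited AEs, "Each AE summary will be displayed by vaccination group and dose regimen". On follow-up beyond 28 days it says "In addition selected AE summary tables will be repeated for unsolicited AEs occurring at any time after the first administration of the trial product".

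Appendix C lists one trial-long severity table, 14.3.1.3.2, titled "Summary of Unsolicited Adverse Events for the Duration of the Trial by Maximum Intensity (Grade) after Any Dose". Nothing in that title limits it to regimens. The shell in Appendix D, headed "Summary of Unsolicited Adverse Events for the Duration of the Trial by Maximum Intensity (Grade) After any Dose", has four columns: 1x1 µg, 2x1 µg, 1x2 µg and 2x2 µg. Its footnote nevertheless reads "Percentages are based on total no. of subjects in each vaccination group". The 28-day counterpart, 14.3.1.2.4 ("Summary of Unsolicited Adverse Events Within 28 Days by Maximum Intensity (Grade) After any Dose"), has columns for 1 µg, 2 µg, 5 µg and Rabipur.

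**The concern.** A programmer works from the shell. Built as drawn, 14.3.1.3.2 leaves out the highest dose level and the active control. No other planned table shows maximum grade over the whole trial. A reader of the report could not set the trial-long severity profile of the 1 µg and 2 µg regimens beside that of 5 µg or Rabipur, for all unsolicited AEs or for related ones. SAP section 12 does not declare this as a change; it mentions only the dropped per-protocol sets.

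**Working it through.** The plan states no figure to reproduce. The check compares the shells with each other and with the text, then counts subjects.

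**1. The unsolicited-AE shells side by side (SAP Appendix D)**

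| Shell | Period | Columns | Grade rows |
|---|---|---|---|
| 14.3.1.2.4 | 28 days, any dose | 1 µg, 2 µg, 5 µg, Rabipur | Yes, all and related |
| 14.3.1.3.1 | Whole trial, any dose | 1 µg, 2 µg, 5 µg, Rabipur | No |
| 14.3.1.3.2 | Whole trial, any dose | 1x1, 2x1, 1x2, 2x2 µg | Yes, all and related |
| 14.3.1.3.3 | Whole trial, any dose | 1 µg, 2 µg, 5 µg, Rabipur, Total | No (SOC and PT) |
| 14.3.1.3.4 | Whole trial, post dose 1 | 1x1, 1x2, 5 µg, Total | No (SOC and PT) |
| 14.3.1.3.5 | Whole trial, post dose 2 CV7202 or dose 3 Rabipur | 2x1, 2x2 µg, Rabipur, Total | No (SOC and PT) |

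Of the five trial-long shells, 14.3.1.3.2 is the only one with grade rows and the only one without both 5 µg and Rabipur.

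**2. Is it a text-extraction artefact?** Unlikely. The header has four columns and each of the six grade rows has exactly four cells.

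**3. Is it a deliberate regimen table?** The documents point the other way.
- Regimen-only shells elsewhere (14.1.2, 14.2.1.2, 14.3.5.2) say so in their titles, and each has a companion by vaccination group (14.1.1, 14.2.1.1, 14.3.5.1). This shell has neither.
- Where a shell stands for further groups, a programming note says so, as in 14.3.1.1.3.1. There is no such note here.
- The footnote bases percentages on the vaccination group, which does not fit regimen columns.

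**4. Which rule is firmer?** Section 6 is, because it makes vaccination group the base display for every summary table. The shells do not follow section 11.2.2 uniformly: 14.3.1.2.4, for example, shows groups and has no regimen version.

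**5. Coverage.** SAP section 6.4 gives the numbers vaccinated at the second interim analysis: 16 (1 µg), 16 (2 µg), 10 (5 µg) and 11 (Rabipur).
- Total: 16 + 16 + 10 + 11 = 53.
- Covered: 16 + 16 = 32, and 32/53 = 60.4%.
- Omitted: 10 + 11 = 21, and 21/53 = 39.6%.
- With the protocol's planned numbers: (10 + 10)/52 = 38.5%.

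**The case against.** The strongest reply is that the plan already requires the missing groups. Sections 6 and 11.2.2 do so in words, section 11.2.2 names mild, moderate and severe events among the items of the overall summary, and Appendix A lets tabulations be reorganised during programming. On this view one layout template fails to follow a sound specification. That stands as a description of the fault: it is an inconsistency, not an analysis decision. It does not remove the need to correct it. The overall summary shell 14.3.1.3.1 has no grade rows either. Appendix A's examples are combining and splitting tables, not supplying missing groups. Section 6 also labels analyses made after SAP finalisation as post hoc, so a late addition might have to be defended.

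The second reply is that little is lost, and this largely stands.
- The intensity endpoint for unsolicited AEs (protocol 4.2, SAP 11.1) covers Days 1–29. Shell 14.3.1.2.4 serves it for all four groups.
- The longer-term endpoints for SAEs, MAAEs and AESIs do not ask for intensity.
- After the 28-day windows, collection narrows to SAEs, MAAEs, withdrawals, AESIs and intercurrent conditions. After Month 12, only vaccine-related SAEs and MAAEs are collected, along with AESIs and intercurrent conditions (protocol 9.2).
- Shells 14.3.1.3.1 and 14.3.1.3.3 give trial-long counts for both omitted groups, and listing 16.2.7.1.1 shows intensity and relationship for each event. A listing is not a tabulation with n (%) by group, but the information is in the report.

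A reader might also infer that the omission hides the reactogenicity that led to lower doses. The documents do not support this. Protocol 5.7 cites reactogenicity and immunogenicity together. Reactogenicity is captured by solicited AEs and the investigator's injection-site assessment, and both are tabulated by grade with 5 µg and Rabipur columns (for example 14.3.1.1.1.5, 14.3.1.1.1.9 and 14.3.5.3).

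**Conclusion.** The shell is wrong against the SAP's own rules. Programmed literally, it leaves 21 of 53 vaccinated subjects (39.6%), comprising the highest dose level and the active control, without a trial-long tabulation of maximum grade. The 39.6% measures absence from one supplementary table, not from the safety reporting. It would be going too far to conclude that a primary endpoint is incomplete or that severity data for these groups are lost or withheld: the endpoint, the solicited reactions, the trial-long counts and the event-level listing are all planned for both groups. The point is minor and worth correcting because the correction is easy.

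This rests on two assumptions: that the 53 vaccinated at the second interim analysis are the final vaccinated number, and that the tables are programmed as drawn.

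**What to change.** Either of two changes will do.
- Add a version of 14.3.1.3.2 by vaccination group, with the columns of 14.3.1.2.4 (1 µg, 2 µg, 5 µg, Rabipur). Keep the present regimen columns as a second table whose title says *by Treatment Group*, and list both in Appendix C.
- Add 5 µg and Rabipur columns to the existing shell.

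The regimen display should stay in either case, because section 11.2.2 asks for both; replacing it with group columns would swap one departure for another. The percentage footnote should name the denominator actually used in each column.

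The cost is one extra table or two extra columns. Coverage rises from 32 of 53 to 53 of 53 subjects, with no new data, derivation or method.
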